7. RANDOMIZATION

The randomization will be stratified by center and will use mixed blocks of 2 and 4 with a 1:1 ratio to ensure even distributions of Active and Control subjects at each site. Trial ulcer size (area) at the time of randomization (2 strata: 1 cm² to ≤ 3 cm² vs. > 3 cm² to 12 cm²) will also be used as a stratification factor to ensure balance between treatment groups in this stratum.

8. BLINDING

Due to the nature of this trial and the product, the subjects, Investigators and personnel involved in this trial cannot be blinded. The assessment of complete wound closure, determination of ulcer area and wound closure parameters will be determined by both the Investigator and by computerized planimetric analysis of 3D digital photographs of the DFU using the 3D LifeViz Micro camera system and DermaPix software developed by QuantifiCare.

9. INTERIM ANALYSIS FOR SAMPLE SIZE ADJUSTMENT

9.1. Interim Prediction for Early Success

A single interim analysis will be performed when 50% of subjects complete the study. By employing a group-sequential design with a Pocock alpha spending function, the following decisions will be made at the interim analysis with respect to the efficacy outcome:

- 1) Stop the study upon demonstrating statistically significant superiority of the Active Treatment (PriMatrix Dermal Repair Scaffold) to the Control Treatment (Standard of Care) if the two-sided p-value testing the stated hypotheses is ≤ 0.031 and the difference is in favor of the Active Treatment (PriMatrix Dermal Repair Scaffold).
- 2) Stop the study upon demonstrating futility of the Active Treatment (PriMatrix Dermal Repair Scaffold) to the Control treatment (Standard of Care) if the two-sided p-value

testing the stated hypotheses is ≤ 0.031 and the difference is in favor of the Control Treatment (Standard of Care).

- 3) Continue the study if the two-sided p-value testing the stated hypotheses is > 0.031 .

With this design and assuming 46% of DFUs managed with the Active Treatment achieve complete wound closure by 12 weeks and 26% achieve complete wound closure when managed with the Control Treatment, the probability of stopping early due to showing superiority with the Active Treatment (PriMatrix Dermal Repair Scaffold) is 0.479. If the decision at the interim analysis is to continue the study, the hypotheses at the end of the study will be tested at a two-sided alpha level of 0.028 to maintain an overall two-sided alpha of 0.05.

Further, conditional power will be calculated at the interim analysis for predicting the final study success. In case more data is needed, sample size re-estimation will be considered in order to meet the final study objective.

Conditional Power

Conditional power: the probability of statistical significance at the completion of the study given the data obtained so far. From Jennison and Turnbull (2000) pages 205 to 208, the general upper one-sided conditional power at stage k for rejecting a null hypothesis about a parameter θ at the end of the study, given the observed test statistic, Z_k , is computed as

$$P_{uk}(\theta) = \Phi\left(\frac{Z_k \sqrt{I_k} - z_{1-\alpha} \sqrt{I_K} + \theta(I_K - I_k)}{\sqrt{I_K - I_k}}\right),$$

the general lower one-sided conditional power at stage k is computed as

$$P_{lk}(\theta) = \Phi\left(\frac{-Z_k \sqrt{I_k} - z_{1-\alpha} \sqrt{I_K} - \theta(I_K - I_k)}{\sqrt{I_K - I_k}}\right),$$

and the general two-sided conditional power at stage k is computed as

$$P_k(\theta) = \Phi\left(\frac{Z_k \sqrt{I_k} - z_{1-\alpha/2} \sqrt{I_K} + \theta(I_K - I_k)}{\sqrt{I_K - I_k}}\right) + \Phi\left(\frac{-Z_k \sqrt{I_k} - z_{1-\alpha/2} \sqrt{I_K} - \theta(I_K - I_k)}{\sqrt{I_K - I_k}}\right),$$

where

θ = the parameter being tested by the hypothesis

k = an interim stage at which the conditional power is computed ($k = 1, \dots, K-1$)

K = the stage at which the study is terminated, and the final test computed

Z_k = the test statistic calculated from the observed data that has been collected up to stage k

I_k = the information level at stage k

I_k = the information level at the end of the study

$1 - z_\alpha$ = the standard normal value for the test with a type I error rate of α .

For a test of two proportions with null hypothesis $H_0: P_1 = P_2$, where P_1 and P_2 are the population proportions in groups 1 and 2, respectively, under the alternative hypothesis, these components are computed in Chang (2008) pages 70 and 71 as

p_{jk} is the sample proportion for group j , estimating P_j at stage k

I_k is the estimated information from the sample at stage k

N_{jk} is the sample size in group j at stage k

N_j is the final sample size in group j

Computing conditional power requires you to set P_1 and P_2 . Their values can come from the values used during the planning of the study, from similar studies, or from estimates made from the data that has emerged.

In addition, an early data review will be performed when 50 patients reach the primary endpoint. The purpose of this review is to ensure the study execution is as originally planned, and therefore, no alpha spending is involved. The review will be involved only blinded data for a purpose of data cleaning and checking. And no statistical tests will be computed.

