	
will be paused once 50 subjects (25 in each treatment arm) have been enrolled in order to perform an early data review and an interim analysis is planned after 128 subjects have completed study participation.
 
Screening Phase – 2 weeks ± 3 days (Max 17 days)          Prior to any study-related procedures, subjects will sign the IRB/IEC approved informed consent form (ICF). Medical history will be obtained and clinical assessments performed to determine subject eligibility. Certain eligibility criteria will be reaffirmed on Screening Visit 2 and Randomization. Photographs and planimetric area evaluation will be performed to document ulcer area before and after debridement. The study ulcer will receive SOC daily for two weeks.
 
Treatment Phase – up to 13 weeks ± 3 days (Max 94 days)
 
Randomization/Treatment Visit 1 (TV1)          Following the two-week screening phase, the subject will return to the clinic and physical assessments will be made to confirm the subject’s final eligibility. The ulcer will be photographed, sharply-debrided (if necessary), and photographed again. Planimetric evaluation will be performed to determine the area of ulcer post debridement. Subjects who meet all eligibility criteria will be randomized 1:1 to receive either Active Treatment or Control Treatment.
 
Treatment Visits 2 through 13          After randomization, subjects will be evaluated weekly (7 ± 3 days). Assessments will include photographs of the study ulcers, investigator assessment of wound closure, and planimetric evaluations of ulcer area. Safety parameters will be documented, and Medical Resource Utilization data will be collected by reviewing subject source documentation and medical records and subject interviews. Subjects will receive Active or Control treatment for up to 13 weeks or until the study ulcer achieves confirmed complete wound closure.
 
Follow-up Phase – 4-weeks ± 3 days (Max 31 days)          Subjects with complete wound closure in the treatment phase will have a final study visit 4-weeks after the closure confirmation visit to evaluate if the ulcer has remained closed.

ENROLLMENT	Up to 30 centers in the US will randomize up to 256 subjects.

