## 8.6. Interim Analysis for Sample Size Adjustment

A single interim analysis will be completed when 50% of subjects complete the study. Employing a group-sequential design with a Pocock alpha spending function the following decisions will be made at the interim analysis with respect to the efficacy outcome:

1. Stop the study due to demonstrating statistically significant superiority of the Active Treatment to SOC if the two-sided p-value testing the stated hypotheses is  $\leq 0.031$  and the difference is in favor of the Active Treatment.
2. Stop the study due to demonstrating futility of the Active Treatment to SOC if the two-sided p-value testing the stated hypotheses is  $\leq 0.031$  and the difference is in favor of SOC.
3. Continue the study if the two-sided p-value testing the stated hypotheses is  $> 0.031$ .

With this design and assuming 46% of DFUs managed with the Active Treatment achieve complete wound closure by Week 12 (or by TV13) and 26% achieve complete wound closure when managed with the Control Treatment, the probability of stopping early due to showing superiority with the Active Treatment is 0.479. If the decision at the interim analysis is to continue the study, the hypotheses at the end of the study will be tested at a two-sided alpha level of 0.028 to maintain an overall two-sided alpha of 0.05.

Further, conditional power will be calculated at the interim analysis for predicting the final study success. In case more data is needed, sample size re-estimation will be considered in order to meet the final study objective.

In addition, an early data review will be performed when 50 patients reach the primary endpoint. The purpose of this review is to ensure the study execution is as originally planned, and therefore, no alpha spending is involved.

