6. SAMPLE SIZE DETERMINATION AND RATIONALE

This is a randomized study with two treatment groups. Assuming:

- 46% of DFUs receiving PriMatrix close by 12 weeks (84 days).
- 26% of DFUs receiving with Standard of Care close by 12 weeks (84 days).

Overall 2-sided Type I Error rate (alpha) of 0.05. Under the above assumptions, 102 subjects per treatment group will be required to meet the Type I error rate of 0.05 and 80% power; for a total

of 204 subjects for the study. As the treatment duration is short, the discontinuation rate is predicted to be around 15%. To accommodate the potential discontinuations, 240 subjects will be randomized (120 per treatment group) to this trial. The subjects will be randomized to the treatment groups in a 1:1 ratio.

A single interim analysis when 50% of subjects complete the trial, using group-sequential methods and Pocock alpha spending function, where the hypotheses will be tested at a two-sided alpha of 0.031 at the interim analysis and at a two-sided alpha of 0.028 at the final analysis.

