9.2. Sample Size Re-Estimation

For sample size re-estimation purposes, conditional power will be calculated at the interim analysis for predicting the probability of the final success. In case that additional data information is needed, appropriate sample size re-estimation will be considered to ensure sufficient data to evaluate the study objectives at the end of the study.

The statistical power at the time of the interim analysis will be calculated using the conditional power approach [Chen et al., 2004]). The formula is listed as following:

$$CP(\tau, Z) = \Phi\{Z_\tau / \sqrt{\tau(1 - \tau)} - Z_\alpha / \sqrt{(1 - \tau)}\}$$

where:

- $CP(\tau, Z)$ is the conditional power at the interim analysis
- $\Phi\{\cdot\}$ is the cumulative distribution function of a standard Normal distribution
- Z_α is the upper α th quintile for standard Normal distribution (i.e. $Z_{0.05}$)
- τ is the information fraction at the interim analysis

$$\tau = (n_t + n_c) / (N_t + N_c)$$

where:

- N_t is the sample size in the treatment group

- N_c is the sample size in the control group
- n_t is the number of subjects in the treatment group at the time of interim analysis
- n_c is the number of subjects in the control group at the time of interim analysis
- Z_τ is Z-score at the information fraction of τ . For binary endpoints, the Z-score will be obtained from the following formula:
 - Superiority (primary efficacy)

$$Z_\tau = \frac{\hat{p}_t - \hat{p}_c}{SE} = \frac{\hat{p}_t - \hat{p}_c}{\sqrt{\hat{\sigma}_t^2/n_t + \hat{\sigma}_c^2/n_c}}$$

where: \hat{p}_t is the estimated mean value in the treatment group at the time of interim analysis, and \hat{p}_c is the estimated mean value in the control group at the time of interim analysis.

The following decision rules will be followed:

- a. If the conditional power is larger than 50%, the sample size may be adjusted upward and no Type I error adjustment will be made to the final analysis [Chen et al., 2004].
- b. If the conditional power is less than 50% then the Type I error rate will be inflated and increase the sample size will be necessary. The total sample size M required to achieve conditional power of CP by assuming the current treatment trend continues is obtained by solving the following equation:

$$Z_{CP} = \frac{Z_\tau/\sqrt{r/M} - Z_\alpha}{\sqrt{(1 - r/M)}}$$

where:

- M: required samples size to achieve the desired CP (i.e., 80%)

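### The interim futility rule is a control-superior boundary, so the plan has no stop for lack of effect; SAP 9.2 rule b then requires a sample-size increase that its equation cannot supply at Z ≤ 0

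*SAP*

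**What the plan says.** SAP 9.1 gives three interim decisions. The first stops for superiority of the active treatment at a two-sided p-value of 0.031 or less. The second reads "Stop the study upon demonstrating futility of the Active Treatment (PriMatrix Dermal Repair Scaffold) to the Control treatment (Standard of Care") and applies the same p-value when the difference favours control. The third continues whenever p exceeds 0.031, in either direction. Protocol 8.6 has the same second decision ("Stop the study due to demonstrating futility of the Active Treatment to SOC if the two-sided p-value testing the stated hypotheses is" at most 0.031, with the difference favouring SOC), and the synopsis repeats it.

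SAP 9.2 then gives conditional-power rules and says they will be followed. Above 50% the sample size may be raised with no Type I adjustment (rule a). Below 50%, "then the Type I error rate will be inflated and increase the sample size will be necessary" (rule b). Under rule b the total M is solved for a desired conditional power of 80%, assuming the current trend continues. No lower limit on conditional power and no upper limit on M is given.

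The opening of 9.2, SAP 9.1 and Protocol 8.6 are softer: re-estimation will be considered if more data are needed. The protocol has no conditional-power decision rule. On size, the SAP plans 240 with an interim after 120. The protocol plans 256 with an interim after 128, and its synopsis says "Up to 30 centers in the US will randomize up to 256 subjects".

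**The concern.** A futility rule is meant to end a trial that is unlikely to succeed. This one acts only when control is significantly better. A product with no effect is therefore almost never stopped. Rule b instead sends it to an enlargement, and in about half of such interims the enlargement cannot be computed.

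Two things are at stake. First, a report could state that the trial had a futility boundary and passed it, when no stop for lack of effect existed. Second, a rule that the SAP says will be followed cannot be followed in the cases where lack of effect is the question. Rule b also acknowledges Type I inflation without saying how the final test would allow for it, although the plan fixes an "Overall 2-sided Type I Error rate (alpha) of 0.05".

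**Working it through.** **Inputs.** SAP 6: "46% of DFUs receiving PriMatrix close by 12 weeks (84 days"), "26% of DFUs receiving with Standard of Care close by 12 weeks (84 days"), 102 per arm evaluable, 240 randomized, and a "two-sided alpha of 0.031 at the interim analysis and at a two-sided alpha of 0.028 at the final analysis". SAP 4: interim after r = 120, so τ = 120/240 = 0.5. SAP 9.2: Z_α = Z_0.05 = 1.645; target conditional power 80%, so Z_CP = 0.842.

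**Reproducing the plan.** Pocock-type spending at τ = 0.5 gives 0.0310 at the interim and 0.0277 at the final look. With 46% vs 26% and 51 per arm (half of 102), the probability of an early superiority stop is 0.478; the plan states 0.479. The two-look power at 102 per arm is 80.3%, and 204/0.85 = 240. The group-sequential figures hold.

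**Decision 2.** Two-sided p ≤ 0.031 favouring control means Z ≤ −2.157. With no effect its probability is 0.031/2 = 1.55%.

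**Where rule b starts.** Conditional power by SAP 9.2 is Φ{Z/√(τ(1−τ)) − Z_α/√(1−τ)}. It equals 50% at Z = Z_α√τ = 1.645 × 0.7071 = 1.163. At Z = 0 it is Φ(−1.645/0.7071) = 0.010. For example, 16/60 vs 16/60 gives Z = 0 and p = 1.0, so the trial continues and rule b applies.

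**Rule b's equation.** Z_CP = (Z√(M/r) − Z_α)/√(1 − r/M).
- If Z ≤ 0, the numerator is negative for every M > r, so the right side can never equal +0.842. No M exists. This holds for any positive Z_α and any r.
- If 0 < Z < 1.163, a root exists and grows as Z falls. At the edge Z = 1.163, M = 502. Check: M/r = 4.184 and its root is 2.0455; (1.163 × 2.0455 − 1.645)/√(1 − 0.239) = 0.734/0.872 = 0.842. M is 697 at Z = 1.0 and 2,926 at Z = 0.5.

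**Sensitivity of the smallest M (at the 50% edge).**

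| Reading | Smallest M |
|---|---|
| r = 120, N = 240, 1.645 (SAP as written) | 502 |
| r = 128, N = 256, 1.645 (protocol sizes) | 535 |
| r = 120, N = 240, 1.960 | 449 |
| r = 120, N = 240, 2.197 (final-look value for 0.028) | 421 |
| r = 102, N = 204, 1.645 | 427 |

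Combining N = 204 with a stricter critical value lowers it further. The lowest value found is 350 (r = 120, N = 204, 2.197), still above 256.

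**How often (60 per arm, normal approximation, 1.645).** The interim Z has mean Δ/SE. For 36% vs 26% this is 0.10/√(0.4228/60) = 1.191; for 46% vs 26% it is 0.20/√(0.4408/60) = 2.333.

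| True rates | Decision 2 | Rule b | of which no M exists |
|---|---|---|---|
| 26% vs 26% | 1.55% | 86.2% | 48.5% |
| 36% vs 26% | 0.04% | 48.8% | 11.6% |
| 46% vs 26% | <0.01% | 12.1% | 1.0% |

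Percentages are of all interims. In the null row, 50% − 1.55% = 48.45% have no solution and 37.76% have M above 502.

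**The other conditional-power method.** SAP 9.1 also allows conditional power with P1 and P2 set at planning values. With 46% and 26%, N = 240 and 1.645, conditional power at Z = 0 is about 50% (50.3% with unpooled variance), against 1% by the 9.2 formula. The method chosen can therefore decide whether rule b applies.

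**The case against.** The strongest objection is timing. SAP version 1.0 is dated 3 August 2020. SAP 10.4 says screening and enrolment were ended before 240, and SAP 11.1.1 puts 207 patients in the primary efficacy population. On these documents re-estimation can no longer enlarge the trial, and a new futility rule would have no enrolment to stop. This stands, and it limits the practical effect. It does not make the label or rule b correct, and the SAP still states both as current.

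Second, three places say only that re-estimation will be considered, so an increase may never have been mandatory. This also stands in part: the SAP contradicts itself, and the passages must be reconciled. The equation fails at Z ≤ 0 on either wording.

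Third, a two-sided group-sequential design without a futility boundary is valid. True: the fault is claiming a futility stop, not lacking one.

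A reader might go further and infer that every negative interim leads to enlargement, that 502 is a firm minimum, or that 256 is a hard ceiling which should also cap rule a. The documents do not support these. A significantly negative interim does stop under decision 2. The 502 depends on r, N and the critical value. The protocol's 256 is its planned size, and Protocol 8.6 itself contemplates re-estimation. Rule a's equation asks for 328 at Z = 1.4 and 277 at Z = 1.5, so a cap at 256 would nearly abolish re-estimation, which is a design trade-off and not a correction.

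**Conclusion.** Decision 2 is mislabelled in both documents, and the plan has no stop for lack of effect. Rule b, followed literally, cannot be carried out at any Z ≤ 0. That result is free of assumptions about r or the critical value. Its frequency, 48.5% of null interims, rests on 60 per arm, the normal approximation and the 9.2 trend formula. For small positive Z the required total is at least about 420 to 535 on the main readings, roughly twice the planned size.

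It would be wrong to infer that the trial was enlarged, or that its interim went badly. The documents report no interim result, no conditional power and no re-estimation decision. With enrolment closed, the remaining consequence is mainly for what the trial may claim about its interim rules. The superiority boundaries and the sample size calculation are not affected.

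**What to change.** 1. In SAP 9.1, Protocol 8.6 and the synopsis, rename decision 2 as control superior, and do not describe the trial as having a futility stop.
2. Withdraw rule b, so that the planned size is kept when conditional power is below 50%. Reconcile the wording on whether an increase is considered or necessary.
3. State whether planning values (9.1) or the current trend (9.2) govern the conditional-power decision.
4. Record in the SAP whether the interim took place, when, and what was decided, and note that enrolment ended before 240 with 207 in the primary set.

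These are wording changes and cost no power. Rule a needs no cap for this purpose.

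Optional, and only if the interim can still act: a non-binding stop at Z ≤ 0. It would stop 50% of null trials instead of 1.55%. Power at 46% vs 26% would fall by about 0.15 percentage points (by simulation, 0.879 to 0.878 at 60/120 per arm and 0.821 to 0.819 at 51/102), with no increase in Type I error.

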9.2. Sample Size Re-Estimation

For sample size re-estimation purposes, conditional power will be calculated at the interim analysis for predicting the probability of the final success. In case that additional data information is needed, appropriate sample size re-estimation will be considered to ensure sufficient data to evaluate the study objectives at the end of the study.

The statistical power at the time of the interim analysis will be calculated using the conditional power approach [Chen et al., 2004]). The formula is listed as following:

$$CP(\tau, Z) = \Phi\{Z_\tau / \sqrt{\tau(1 - \tau)} - Z_\alpha / \sqrt{(1 - \tau)}\}$$

where:

- $CP(\tau, Z)$ is the conditional power at the interim analysis
- $\Phi\{\cdot\}$ is the cumulative distribution function of a standard Normal distribution
- Z_α is the upper α th quintile for standard Normal distribution (i.e. $Z_{0.05}$)
- τ is the information fraction at the interim analysis

$$\tau = (n_t + n_c) / (N_t + N_c)$$

where:

- N_t is the sample size in the treatment group

- N_c is the sample size in the control group
- n_t is the number of subjects in the treatment group at the time of interim analysis
- n_c is the number of subjects in the control group at the time of interim analysis
- Z_τ is Z-score at the information fraction of τ . For binary endpoints, the Z-score will be obtained from the following formula:
 - Superiority (primary efficacy)

$$Z_\tau = \frac{\hat{p}_t - \hat{p}_c}{SE} = \frac{\hat{p}_t - \hat{p}_c}{\sqrt{\hat{\sigma}_t^2/n_t + \hat{\sigma}_c^2/n_c}}$$

where: \hat{p}_t is the estimated mean value in the treatment group at the time of interim analysis, and \hat{p}_c is the estimated mean value in the control group at the time of interim analysis.

The following decision rules will be followed:

- a. If the conditional power is larger than 50%, the sample size may be adjusted upward and no Type I error adjustment will be made to the final analysis [Chen et al., 2004].
- b. If the conditional power is less than 50% then the Type I error rate will be inflated and increase the sample size will be necessary. The total sample size M required to achieve conditional power of CP by assuming the current treatment trend continues is obtained by solving the following equation:

$$Z_{CP} = \frac{Z_\tau/\sqrt{r/M} - Z_\alpha}{\sqrt{(1 - r/M)}}$$

where:

- M: required samples size to achieve the desired CP (i.e., 80%)
- $\Phi(Z_{CP})$ is the cumulative standard normal distribution evaluated at Z_{CP}
- $r = n_T + n_c$ is total number of subjects at the time of interim analysis

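### SAP 9.2 computes conditional power and the new sample size against Z0.05 although the final test is two-sided 0.028, and rule b admits Type I inflation without an adjusted test or a maximum N

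*SAP*

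**What the plan says.** The final test is fixed in two places. SAP 6 carries it out "at a two-sided alpha of 0.028 at the final analysis", and SAP 9.1 says the hypotheses "will be tested at a two-sided alpha level of 0.028 to maintain an overall two-sided alpha of 0.05". Protocol 8.3 and 8.6 agree.

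SAP 9.1 then defines the quantity of interest: "Conditional power: the probability of statistical significance at the completion of the study given the data obtained so far". Its formulas leave the level open, describing the critical value only as "the standard normal value for the test with a type I error rate of" alpha, with no 0.028 beside it.

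SAP 9.2 prints a second conditional power formula. There Z_alpha is the upper-alpha "quintile for standard Normal distribution (i.e", and the bracket continues with Z0.05. Two decision rules rest on that formula:

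- **Rule a, CP above 50%:** "the sample size may be adjusted upward and no Type I error adjustment will be made to the final analysis".
- **Rule b, CP below 50%:** "If the conditional power is less than 50% then the Type I error rate will be inflated and increase the sample size will be necessary". For the desired CP (80%), the total M "by assuming the current treatment trend continues is obtained by solving the following equation", and that equation uses the same Z_alpha.

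Neither document gives an adjusted critical value, a weighted or combination test, or a maximum M.

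**The concern.** There are two separate faults.

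**(a) Wrong critical value.** Section 9.2 calculates the chance of crossing a threshold that the trial does not use. Every interim CP computed from it is too high, the 50% switch is misplaced, and M is too small for the power it claims.

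**(b) Conceded inflation.** Rule b says Type I error will be inflated and goes ahead with the increase. The 0.028 level is justified only by two-look Pocock spending at the planned size. Without an adjusted final test or a maximum M, the statement in 9.1 that 0.05 is maintained has no support once rule b is used.

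At stake are the accuracy of any interim CP that is reported and the SAP's claim that its printed rules preserve 0.05.

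**Working it through.** **Inputs.** Closure 46% vs 26%, 102 evaluable per arm, 240 randomized (SAP 6). Interim at half information, t = 0.5. Nominal two-sided levels 0.031 and 0.028, so the bounds are 2.157 and 2.197. Z0.05 = 1.645. For re-estimation, r = 120 at the interim and N = 240.

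**1. The plan's own figures reproduce.** Pocock-type spending at t = 0.5 gives nominal levels 0.0310 and 0.0277 (rounded to 0.028). With those bounds, pooled variance and 102 per arm, power is 0.803 and the chance of stopping early for superiority is 0.479, as stated. Overall two-sided alpha with the rounded bounds is 0.0502. So 2.197 is the critical value the design needs.

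**2. Where the 50% switch falls.** CP = Φ(Z/√(t(1−t)) − z/√(1−t)), which is 50% when Z = z√t.

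- Printed: 1.645 × 0.7071 = 1.163.
- Actual test: 2.197 × 0.7071 = 1.554.

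To express these as closure rates, solve (p − 0.26)/√((p(1−p) + 0.26×0.74)/60) = Z. With 60 per arm and 26% on control, p = 35.8% and 39.2%.

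**3. How far CP is overstated.**

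| Interim Z | CP as printed | CP against 2.197 |
|---|---|---|
| 1.0 | 37.2% | 13.4% |
| 1.163 | 50.0% | 21.7% |
| 1.3 | 60.8% | 30.6% |

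Under 46% vs 26%, the mean interim Z is 0.20/√((0.46×0.54 + 0.26×0.74)/n), which is 2.333 for n = 60 per arm and 2.151 for n = 51. The chance of Z between 1.163 and 1.554, where CP is read as above 50% but is below it, is 0.097 and 0.114 respectively.

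**4. What M delivers.** Solve (Z/√(r/M) − z)/√(1 − r/M) = 0.8416 with z = 1.645. Then evaluate the left side at that M with z = 2.197 and take Φ.

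| Interim Z | M as printed | M needed with 2.197 | CP delivered by printed M |
|---|---|---|---|
| 0.5 | 2,926 | 4,399 | 60.9% |
| 1.0 | 697 | 1,073 | 59.3% |
| 1.163 | 502 | 784 | 58.3% |

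At Z = 0.1, M is 74,150 (61.4% delivered). For Z ≤ 0 there is no finite M. The smallest M under rule b is 502, and 502/240 = 2.09.

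**5. Type I error.** Under no effect, the rule-b zone (−2.157 < Z < 1.163) has probability 0.862. M is finite only for 0 < Z < 1.163, probability 0.378. For final size m, the chance of a final rejection in favour of active, given Z, is 1 − Φ((2.197√m − Z√120)/√(m − 120)); the lower tail is analogous. Integrate both over the interim Z and add the interim crossings.

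Because the SAP is silent, the rule-b rows assume that rule b is applied whenever M is finite, the final test stays at 2.197, and N is unchanged for Z ≤ 0. The caps are also assumed; both always bind, since M is never below 2.09 × 240.

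| Scenario | Two-sided Type I error | Upper tail |
|---|---|---|
| No increase | 0.0502 | 0.0251 |
| Rule a as printed | 0.0504 | 0.0252 |
| Rule b, cap 1.5 × 240 | 0.0525 | 0.0269 |
| Rule b, cap 2 × 240 | 0.0537 | 0.0277 |
| Rule b, no cap | 0.0575 | 0.0292 |
| 2.197 in both equations, increase only for CP 50–80% | 0.0499 | 0.0248 |

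**6. The trial as it ran.** SAP 11.1.1 puts 207 in the primary efficacy population. With no increase and the same bounds, a bivariate normal with correlation √(r/207) gives overall two-sided alpha 0.0486 for r = 120 (the SAP's interim size) and 0.0477 for r = 128 (the protocol's).

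**The case against.** The strongest reply is that this text can no longer operate. SAP version 1.0 is dated 03AUG2020, after the 3 March 2020 randomization cut-off, and SAP 10.4 already records that enrolment ended short of 240. That stands and limits the weight of the point. It does not make the formula right or reconcile rule b with 9.1.

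Other replies:

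- **Z0.05 may have been meant as 1.960.** The SAP does not print 1.645; it follows from the upper-alpha definition. With 1.960 the switch is at Z = 1.386, where CP against 2.197 is 37%. The error is smaller but remains.
- **Rule b omits an adjustment and does not rule one out.** That is a fair reading, since only rule a says no adjustment is made. But a rule that announces inflation and supplies no remedy cannot stand beside a claim that 0.05 is maintained.
- **The only maximum in the documents is the protocol's 256.** Used as a cap, it brings rule b to about 0.0505, a negligible rise. But 256 is the planned enrolment, differs from the SAP's 240, and is not tied to re-estimation.
- **No passage says that CP will be reported as a result.** True. The SAP does require it to be calculated at the interim, and the decision rules depend on it.
- **An adjusted final test would also cure rule b.** Agreed, but with enrolment over it would serve no purpose here.

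**Conclusion.** The point holds and should be corrected. Section 9.2 does not compute the conditional power that 9.1 defines. At half information its 50% switch is 0.39 too low on the Z scale (1.554 − 1.163), it reads 50% where current-trend CP is 22%, and its M for 80% delivers 58–61% in the rule-b zone. These figures take Z0.05 literally as 1.645 and assume an interim at half information.

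Rule b is the part that conflicts with alpha; rule a adds almost nothing. The rise to 0.0525–0.0575 is a scenario resting on the assumptions in step 5, not a property of the trial as run.

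Final enrolment below 240 means no increase above that number took effect. The figures of 0.0486 and 0.0477 assume an interim at 120 or 128, and the documents do not report that it was held. Nothing here shows that the final test exceeds 0.05.

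**What to change.** 1. In SAP 9.2, set Z_alpha to the upper 0.014 quantile (2.197) in both the CP formula and the equation for M. In SAP 9.1, state alpha = 0.028 for the two-sided formula.
2. Replace rule b with no increase when CP is below 50%. Alternatively, because enrolment ended below 240, delete rules a and b and, if it is the case, state that no increase was made.

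The cost is SAP wording only. Any interim CP reported becomes less favourable once 2.197 is used, and the option to enlarge the trial below 50% CP is given up.
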